## **Analysis for Exploratory outcomes**

The incidence of a composite of opioid-related complications will be assessed using a log-binomial model and reported as relative risk. The effect on opioid medication use (morphine equivalents) at three months after surgery will be assessed using a t-test or linear regression on the log-transformed opioid consumption. Covariate adjustment will be used to adjust for confounding as needed. The analyses will be carried out at the 95% confidence level.

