## Summary of Changes:

May 12, 2021

- 1- Study title changed to “The effect of preoperative patient education: a randomized trial” (page 1)
- 2- Exploratory aim 2 is taken out on page 9
- 3- Laparoscopy assisted colorectal surgeries added in inclusion criteria on page 9.
- 4- For the brief introduction page, instead of “continue” or “stop”, patients will be presented the options “agree” or “disagree” (page 10)

December 1, 2021

- 1- A change in the inclusion criteria number 4 : from laparoscopic assisted **colorectal**, to laparoscopic assisted **abdominal** surgeries. (Page 9)

August 19, 2022

Sample sized increased to 760 after second interim analysis to compensate the technical data loss.

January 4, 2023

Sample size increased to 1060 after third interim analysis. As it was planned we re-estimated the coefficient of variation (CV) and assuming a 10% drop-out rate, we would need 1060 patients total.

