### b) Opioids as Analgesics and Drawbacks

Opioids remain the mainstay pharmacologic approach to postoperative pain. However, sole reliance on opioid therapy is often inadequate. Most patients report moderate-to-severe pain after surgery despite being given on-demand analgesics. In a 2014 survey, 86% of patients reported postoperative pain and 65% reported pain as

moderate to extreme. Equally concerning is that 74% reported substantial pain even after discharge.

Opioids are associated with multiple perioperative side effects. Many are due to the non-specific binding of opioids to various mu-opioid receptors throughout the peripheral and central nervous system. Such effects include nausea/vomiting, constipation, pruritus, urinary retention, ileus and respiratory depression. A remarkable four-fifths of adults given postoperative opioids report at least one opioid-related complications, with the most common being drowsiness (56%), constipation (35%), and nausea (28%). The most feared complication is respiratory depression which is an important source of adverse events in hospitalized patients. Respiratory depression is common in the postoperative period and is largely unrecognized, causing significant hypoxemia and potential harm.

Opioids are also associated with post-discharge complications. Patients are typically given prescriptions for opioids to alleviate acute surgical pain but many continue to take opioids beyond their recovery period. According to one study on opioid-naïve patients after total hip or knee arthroplasty, 8% of TKA and 4.3% of THA patients continued to use opioids 6 months after surgery. Among patients who used opioids at baseline, 53% of TKA and 35% of THA patients continued using opioids at 6 months. Additionally, long term exposure to opioids may actually prolong pain after surgery by provoking hyperalgesia. Chronic exposure to opioids is immunosuppressive and may augment infection risk.

Another terrifying aspect of long-term opioid use is the risk of tolerance and addiction by the patient, and misuse by the patient's family members, sometime encouraged by multitude of providers giving postoperative patients opioid prescriptions. It is likely that all these factors contribute to the current opioid epidemic.

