### ***Exploratory Aim***

*Exploratory Aim:* To evaluate the effect of analgesic education on composite of opioid-related complications including nausea, emesis, urinary retention, and ileus.

Hypothesis. Patients assigned to analgesic education have fewer composite of opioid-related side effects (i.e. incidence of emesis, nausea, ileus, urinary catheterization, and use of anti-emetics).

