#### ***F. Measurements***

Demographics and comorbidities (*Table 1*) will be obtained from electronic medical reports. Blinded clinical evaluators will query patients for outcomes. Clinicians including nurses will be blinded to study and will be required to perform routine clinical management after surgery. Patients will be followed for outcomes daily for up to 72 hours after surgery. Any opioids prescriptions at discharge will be at the discretion of the primary care team. Long-term outcomes including modified brief pain inventory scores and the use of analgesics will be collected 90 days after surgery by telephone.

*Primary outcome* is opioid consumption during the initial 72 hours after surgery, will be collected from electronic medical records if discharged will be approached by phone and converted to morphine equivalent. Differences in morphine equivalents of 20% or more will be interpreted as clinically meaningful.

*Secondary Aim 1*; satisfaction with post-operative pain management will be evaluated using a 0-10 Likert scale (where 0 means not satisfied at all and 10 means

completely satisfied) on the third day after surgery by phone by blinded clinical evaluators. Difference of 2 points in satisfaction will be accepted as clinically meaningful difference.

**Secondary Aim 2;** pain scores will be obtained from electronic medical records which are recorded by nursing, in PACU it is every 15 minutes and in ward every 4 hours while hospitalized. Difference of 1.2 points in pain scores will be accepted as clinically meaningful difference.

**Exploratory Aim 1;** composite of opioid related side effects and the antiemetic use will be obtained from nursing and medication notes from electronic medical records.

**Exploratory Aim 2;** analgesic use will be obtained from the Ohio prescription

Sex
Age (years)
Ethnicity
Height (cm)
Weight (kg)
BMI
ASA status
Surgery Type
Smoking status (current, former, never)
Medical History : Pulmonary disease, Kidney disease, Hypertension, Diabetes Mellitus, Neurologic disease, Coronary Artery Disease, Myocardial infarction, Chronic pain conditions, illegal drug usage, alcohol abuse, previous surgery or stent placement and medication usage

registry at 3 months.

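### Three-month opioid use is in no listed aim but is still measured and analysed, with source and window unsettled and a log-scale test that cannot take zero use

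*Combined protocol and SAP*

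**What the plan says.** The Exploratory Aim section lists a single aim: "To evaluate the effect of analgesic education on composite of opioid-related complications including nausea, emesis, urinary retention, and ileus". Neither the primary aim nor the two secondary aims mention opioid use beyond the first three days.

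Section F (Measurements) nevertheless carries an item labelled Exploratory Aim 2, for which "analgesic use will be obtained from the Ohio prescription" registry at 3 months. The same section says, of long-term outcomes generally, that "modified brief pain inventory scores and the use of analgesics will be collected 90 days after surgery by telephone".

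The section Analysis for Exploratory outcomes then prescribes a method: the effect on opioid use in morphine equivalents "at three months after surgery will be assessed using a t-test or linear regression on the log-transformed opioid consumption". It names no treatment of zero values. The Secondary Analysis section, by contrast, offers a rank-sum test when satisfaction or pain scores are skewed.

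The only figures on late opioid use are in the background, for arthroplasty patients at six months. Among the opioid-naive, "8% of TKA and 4.3% of THA patients continued to use opioids 6 months after surgery". Among those already using opioids at baseline, the figures are 35% (hip) and 53% (knee).

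**The concern.** Three things are unsettled. A reader cannot tell whether three-month opioid use is an outcome of this trial. If it is, the quantity is undefined: telephone reports and registry records measure different things, and use at three months could mean what a patient takes at that point or everything since surgery. And the prescribed analysis has no place for a patient who uses none.

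The third matters most, because the background argues that education may reduce long-term as well as short-term opioid use. A patient who stops is a success of the intervention, and that patient has no value on the log scale. An analyst must then either drop non-users, which compares groups formed by something the intervention may have changed, or add a constant that the plan does not name. Both choices would be made with the data in hand.

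**Working it through.** **Aims, measurement and analysis side by side.** All three are current text.

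- Aims: one exploratory aim, the complication composite.
- Section F: a second exploratory item, analgesic use at 3 months from the registry, plus a telephone contact at 90 days that also asks about analgesics.
- Analysis for Exploratory outcomes: a log-scale comparison of three-month morphine equivalents.

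The Summary of Changes records "Exploratory aim 2 is taken out on page 9". That may explain how the mismatch arose, but the point does not rest on it: the current sections disagree among themselves.

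**Patients with a defined log value.** The plan gives no sample size, power or event rate for this outcome, so it has no figure of its own to reproduce. Inputs:

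- Total 1060, less the 10% drop-out in the third interim re-assessment: 1060 × 0.90 = 954, or 477 per arm. That drop-out was set for the 72-hour outcome and is borrowed here.
- Share still using: the six-month hip figures, 4.3% (opioid-naive) and 35% (baseline users), as an assumed proxy for three months. The 20% row is a further assumption.
- Log SD: √ln(1 + CV²) with the re-estimated CV of 1.30 gives √ln(2.69) = 0.995, borrowed from the 72-hour outcome. As a check on this conversion, CV 1.00 gives SD 0.833 and a t-based total of 588 for a ratio of 0.80 at 90% power, which is the plan's figure.

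Defined values = 954 × share. Power for a ratio of 0.80 with k users per arm is Φ(|ln 0.80| / (0.995 × √(2/k)) − 1.96).

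| Share using | Defined | Zeros | Power, users only |
|---|---|---|---|
| 4.3% | 41 | 913 | 11% |
| 20% | 191 | 763 | 34% |
| 35% | 334 | 620 | 54% |
| 100% | 954 | 0 | 93% |

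**If non-users are dropped.** Suppose education cuts users from 20% to 13.3% and the dose among users is unchanged (assumed). In simulation with 477 per arm, the users-only ratio is 1.00, with about 5% rejections. The test sees nothing, although the relative risk of any use is 13.3/20 = 0.67. A comparison of proportions in the same scenario has pooled share 0.1665 and standard error √(0.1665 × 0.8335 × 2/477) = 0.0241, so z = 0.067/0.0241 = 2.78 and power is Φ(2.78 − 1.96), about 79%.

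**If a constant c is added.** The log ratio is then (0.133 − 0.200) × (mean of ln(dose + c) among users − ln c). With an assumed median of 300 mg and c = 0.01, this is about −0.067 × (5.70 + 4.61) = −0.69, a ratio of 0.50. Simulation gives 0.50, 0.59, 0.68 and 0.79 for c = 0.01, 0.1, 1 and 10. The rejection rate hardly moves (76% to 81%), so the constant governs the reported effect size more than the test.

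**The case against.** The strongest objection is that the zeros may be few. If the outcome is cumulative dispensing since surgery, which the registry sentence allows, most patients could have a positive value, because the background describes opioid prescriptions after surgery as typical. The counts above would not apply, and a yes/no outcome could sit near its ceiling. This stands, and it is why the window must be defined before the method is chosen. It does not rescue the plan, because some zeros remain likely and the text provides for none.

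It is also fair that the plan does not say non-users are dropped. It is silent, and an added constant is equally compatible with the text. Each route has its own defect, as shown above.

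A reader might infer that the two sources conflict. The documents do not go that far. The registry is attached to the labelled exploratory item, while the telephone sentence covers long-term outcomes in general and analgesics of any kind. They could be complementary. What is missing is a rule for which one supplies the analysed value.

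Finally, the outcome is exploratory. That stands and limits the weight of the point.

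**Conclusion.** The point holds as a minor one. Three-month opioid use sits outside the listed aims but inside the measurement and analysis sections. Its source and window are not fixed, and the stated log-scale analysis cannot include patients with zero use.

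The size depends on assumptions. If current use is meant and the six-month hip figures carry over, about 41 to 334 of 954 patients would enter a users-only test. If cumulative dispensing is meant, far more could.

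Two stronger readings are tempting and are not supported:

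- That a large majority of patients would have zero use. The documents give no three-month figure and none at any time for abdominal surgery, one of the two enrolled populations. The 4.3% and 8% figures are for opioid-naive patients at six months, and the 8% is for knee surgery, which this trial does not enrol. The exclusion criterion removes only sustained use at 15 mg per day or more, so lighter users stay eligible.
- That the test would show apparent harm. If education stopped exactly the lowest-dose quarter of users and the log SD were 1, the users-only ratio would be exp(0.3178/0.75) = 1.53. That stopping pattern and that SD are not in the documents. With the dose among users unchanged, the effect is missed, not reversed.

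The primary and secondary conclusions are not affected.

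**What to change.** Choose one of two routes.

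1. Delete the three-month outcome from section F and from Analysis for Exploratory outcomes, so that both match the aims. The question of zeros then falls away.
2. Restore it as an exploratory aim, with one named source and a defined window, for example current use at 90 days. Make the main analysis any use versus none in all randomised patients with data, reported as a relative risk from the log-binomial model already planned for the composite. Report amount among users descriptively, or add a rank-based comparison that keeps the zeros. If cumulative dispensing is the chosen endpoint, make the rank-based comparison the main analysis, because any use could be near ceiling.

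Either route changes wording only and needs no new data. The price of the second is that some dose information leaves the main exploratory comparison. The choice of source, window and method should be recorded before the three-month data are examined by group.

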## **Interim Analysis**

Three interim analyses will be conducted at 25%, 50% and 75% of the planned enrollment to assess efficacy utility using a group sequential design with a gamma spending function (Gamma = -4 for efficacy and Gamma = -1 for futility) with non-binding efficacy and futility boundaries. The probability of crossing either the efficacy or futility boundary at the first, second and third interim analysis will be 9%, 40% and 78% respectively if the alternative hypothesis is true.

### ***H. Sample Size Calculations***

The coefficient of variation (CV) for cumulative opioid consumption was estimated to be 1.32 using a previous study. However, for our sample size calculations, we assume a lower CV of 1.00 because--unlike the previous study--we will be excluding patients with a history of opioid use in the past 3 months.

Based on the primary outcome of cumulative opioid consumption during the first 72 post-operative hours and assuming a CV of 1.00 we would need a total of 588 patients to have 90% power to detect a 20% decrease in opioid consumption at the 0.05 significance level. Planning for 3 interim analyses and one final analysis, we would require a maximum of **672 patients**. The boundaries for the analysis [efficacy (futility)] are:  $P \leq 0.002$  ( $P > 0.926$ ),  $P \leq 0.005$  ( $P > 0.624$ ),  $P \leq 0.015$  ( $P > 0.2011$ ), and  $P \leq 0.044$  ( $P > 0.044$ ).

**Internal Pilot Study to Re-assess Variability in Primary Outcome.** The coefficient of variation will be re-assessed via an internal pilot study at 50% of the planned enrollment, and sample size will be increased if needed. For a CV of 1.32 and planning for three interim analyses and one final analysis, we would need a maximum of **974 patients**.

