## **ii. Exclusion criteria**

1. Opioid use for more than 30 consecutive days within three preoperative months, at a daily dose of 15 mg or more of morphine or equivalent. ;
2. Regional block or epidural analgesia.

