#### **Primary Analysis**

The effect of pre-operative patient education on cumulative opioid consumption (morphine equivalents) during first 72 postoperative hours will be assessed by using a t-test on the log transformed opioid consumption. Linear regression will be used to adjust for imbalance if necessary. The 95% CI for the ratio of geometric means (intervention/placebo) between the two groups will be reported.

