**Third interim analysis re-assessment:**

It was planned that we would re-estimate the coefficient of variation (CV) at 50% of planned enrollment. From the current sample of patients, the CV was estimated as 1.30 (up from 1.00). Using the re-estimated CV and assuming a 10% drop-out rate, we would need 1060 patients total (530 in each group) in order to have 90% power to detect a geometric mean ratio of 0.80 at a significance level of 0.05.

[figure not shown]

Figure 1: Efficacy and futility boundaries (non-binding) for the study design

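### The sample-size rationale says recent opioid users are excluded, but exclusion criterion 1 admits shorter or lower-dose use, and preoperative opioid use is not a fixed covariate in the primary model

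*Combined protocol and SAP*

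**What the plan says.** Section H (Sample Size Calculations) of the combined protocol and SAP states that the CV for cumulative opioid consumption "was estimated to be 1.32 using a previous study". It then says that "for our sample size calculations, we assume a lower CV of 1.00". The only reason given is that, "unlike the previous study--we will be excluding patients with a history of opioid use in the past 3 months".

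The exclusion criteria in the Setting and Population section are narrower. Criterion 1 reads: "Opioid use for more than 30 consecutive days within three preoperative months, at a daily dose of 15 mg or more of morphine or equivalent". Duration and dose must both be met. The only other exclusion is regional block or epidural analgesia, and no inclusion criterion concerns opioid history.

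The Primary Analysis is a "t-test on the log transformed opioid consumption", with linear regression to adjust for imbalance if needed. Section G adjusts all analyses for baseline characteristics whose absolute standardized difference (ASD) exceeds 0.10. Table 1 lists chronic pain conditions and medication usage, but does not name preoperative opioid use or dose. The Intervention section stratifies randomization by chronic pain only.

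The third interim re-assessment reports a CV of 1.30 and sets enrolment at 1060, allowing 10% drop-out, for "90% power to detect a geometric mean ratio of 0.80 at a significance level of 0.05".

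**The concern.** The sample-size rationale and the eligibility criteria describe different populations. Under criterion 1, a patient taking 10 mg/day for the whole three months is eligible, and so is a patient taking a higher dose for up to 30 days. A reader who relies on section H would take the result as applying to patients with no recent opioid use.

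The second issue is the analysis. Preoperative opioid use is a plausible predictor of postoperative opioid consumption. The plan neither balances it by stratification nor fixes it in the model. It would be adjusted for only if it was captured under medication usage and its ASD passed 0.10. Otherwise, any variance it explains stays in the error term and any chance imbalance below the threshold stays in the estimate.

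**Working it through.** **Inputs from the documents.** CV 1.32 (previous study), 1.00 (planned) and 1.30 (re-estimated); geometric mean ratio 0.80; 90% power; alpha 0.05, taken as two-sided because that reproduces the plan's figure; 1:1 allocation; 588 patients for a fixed design, 672 with three interim analyses; 1060 enrolled with 10% drop-out, so 1060 × 0.90 = 954 evaluable.

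**1. Reproducing the plan.** On the log scale, SD = √ln(1 + CV²) and the difference is |ln 0.80| = 0.223.
- CV 1.00: SD = √ln 2 = 0.833. The t-test calculation gives 588, as stated.
- The plan's own inflation for the interim analyses is 672/588 = 1.143.
- CV 1.32: SD = 1.004, fixed total 854, and 854 × 1.143 = 976 (stated 974).
- CV 1.30: SD = 0.995, fixed total 838, 838 × 1.143 = 958, and 958/0.90 = 1064 (stated 1060).

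**2. What the lower CV was worth, and whether it has been repaired.** It cut the planned maximum from 974 to 672, a difference of 302. Dividing N by 1.143 to get the equivalent fixed design, power at CV 1.30 is about 78% with 672 patients and about 90% with 954 evaluable. The re-estimation has restored the planned power.

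**3. How often the ASD rule would act.** Under simple 1:1 randomization with 954 patients, the SD of a baseline standardized difference is about √(4/954) = 0.065. Then 0.10/0.065 ≈ 1.54, so chance alone takes the ASD above 0.10 in about 12% of trials. In about 88% the rule would leave preoperative opioid use out of the model even if it had been recorded.

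**4. What a fixed covariate might gain (assumptions, not document figures).** Let p be the share of permitted users and r the ratio of their geometric mean consumption to that of the others. Share of log-scale variance explained = p(1 − p)(ln r)² / SD², with SD² = ln(1 + 1.30²) = 0.990.

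| p | r = 1.5 | r = 2 | r = 3 |
|---|---|---|---|
| 10% | 1.5% | 4.4% | 11.0% |
| 20% | 2.7% | 7.8% | 19.5% |
| 30% | 3.5% | 10.2% | 25.6% |

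At p = 20% and r = 2: 0.16 × 0.480/0.990 = 0.078. The standard error shrinks by a factor √(1 − 0.078) = 0.96. In patients, 954 × (1/(1 − 0.078) − 1) ≈ 80.

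**5. How much imbalance could pass unadjusted.** In the same case, an ASD just under 0.10 shifts the log ratio by 0.10 × √(0.2 × 0.8) × ln 2 = 0.10 × 0.40 × 0.693 = 0.028. The standard error of the log ratio is 2 × 0.995/√954 = 0.064, so the shift is about 0.43 of a standard error. This limit holds only if the variable is recorded and the rule is applied to it.

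**The case against.** The strongest reply is that the population is defined by the eligibility criteria, the sentence in section H is only a rationale, and its numerical effect has gone. CV re-estimation was prespecified, the maximum for CV 1.32 was given in advance, and enrolment is now 1060. Any variance from permitted users is already inside the 1.30. That stands: there is no power shortfall, and the 80 patients are an optional gain in precision. It does not make the rationale true.

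Three stronger readings are tempting, and the documents do not support them.
- *That there is no adjustment at all.* The ASD rule, the listed medication usage and the stratification by chronic pain offer partial, conditional protection. What is missing is unconditional adjustment.
- *That a CV of 1.30, so close to 1.32, shows the exclusion failed.* The cited study's title describes hip surgery under spinal anaesthesia. This trial also enrols laparoscopy-assisted abdominal surgery, leaves analgesia to clinicians and collects post-discharge use by phone. Any of these could raise the CV. The documents cannot show why it did not fall.
- *That home opioid inflates the primary total whatever the video does.* The outcome definition has no rule for home opioid, so its inclusion is an inference. The education video covers sparing use of opioids, so home use could itself respond.

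The practical objection also has force. Criterion 1 needs only a yes/no check against a threshold, so lower or shorter use may not have been recorded in analysable form. And the current version follows the third interim analysis, so a change to the primary model is late.

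**Conclusion.** The contradiction between section H and exclusion criterion 1 is certain from the text, and no other eligibility criterion closes it. Its sample-size consequence has been repaired.

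What remains in the analysis is a modest weakness: a plausible predictor of the primary outcome that the stated rule would leave unadjusted in about 88% of trials, assuming simple randomization and 954 evaluable patients. Stratifying by chronic pain helps only as far as chronic pain tracks opioid use. Because allocation is randomized, the effect is lost precision and exposure to chance imbalance, not systematic bias between arms.

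The size of the possible gain is unknown. The 7.8% central case and its range rest wholly on an assumed share of users and an assumed consumption ratio, and should be read as illustration. The point deserves action because correction is cheap, not because the trial's validity is in doubt.

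**What to change.** 1. Reconcile section H with exclusion criterion 1, so that the sample-size rationale and the trial report describe the patients actually enrolled. Which eligibility rule applies is for the sponsor to settle.
2. Before any further unblinded analysis, prespecify preoperative opioid use (none, or some below the exclusion threshold) as a fixed covariate in the log-scale primary regression, whatever its ASD. Take it from the medication history already reviewed for eligibility, and name it in Table 1.
3. Where the data allow, add a sensitivity analysis in patients with no opioid use in the three months before surgery. This addresses the population that section H describes.

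The cost is a wording change, some record extraction for use below the threshold, and a documented late change to the primary model. The amendment should state that the change rests on the mismatch between the two sections and not on interim results. No extra patients are needed.
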